12.10.7.4 Reporting

All AEs that occurred during this clinical study will be recorded on the AE CRF using a recognized medical term or diagnosis that accurately reflects the event. For each adverse event, the investigator will provide the onset date, end date, intensity, treatment required, outcome, seriousness, and action taken with the investigational drug. The PI or designee will review each event and assess its relationship to drug treatment (likely, probably, possibly, unlikely or unrelated). Each sign or symptom reported will be graded in accordance with CTCAE (version 5), and the date of onset, time of onset, and outcome of each event will be noted. To fulfil the regulatory requirements for expedited safety reporting, the sponsor evaluates whether a particular AE is "listed" (i.e. known side effect of the drug or not). Medical judgment should be used to determine the causal relationship of adverse event, considering all relevant factors, including pattern of reaction, temporal relationship, de-challenge or re-challenge, confounding factors such as concomitant medication, concomitant diseases and relevant history. Serious AEs that are considered related to S48168 will be considered a suspected unexpected serious adverse reaction (SUSAR). Assessment of causal relationship must also be recorded on the CRF. If an AE has not resolved at the end of the study reporting period it will be documented as ongoing on the corresponding CRF.

Prompt reporting of adverse events is the responsibility of the PI or designee. The reporting period for AEs is the period immediately following each study administration through 28 days after each dose. AEs must be followed until resolution or stabilization, the subject is lost to follow-up, even if this extends beyond the 28-day post-dosing reporting period (for the purpose of obtaining a stop date for the event).

If an AE has not resolved at the end of the study reporting period it will be documented as ongoing on the corresponding CRF.

Each AE will be reviewed with the medical monitor, [REDACTED] and discussed with the PI. AEs will be reported to the DSMB, regardless of PI classification for review.

The AE severity definitions of CTCAE version 5 will be used for rating the severity of all AEs (Grade 1-5).

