- d: Samples for serum chemistry will be obtained following a fast of at least 10 hours, however, in case of dropouts or rechecks, subjects may not have fasted for 8 hours before the serum chemistry sample is taken. FSH and HbA1c are only required at screening.
- e: AE's will be monitored throughout the study. Study Investigators will attempt to contact all subjects who received at least one dose of study drug (including subjects who terminate the study early) using their standard procedures on Days 7 and 21 (\pm 2 days) whilst on study drug and on Days 35 ± 2 and 42 ± 2 (Follow-up) to determine if any AE has occurred since the last study visit. A compliance assessment will be conducted as a part of the Day 7 and Day 21 contact. Subjects will enter daily log of symptoms as well as study drug intake in a diary for the days when direct communication is not done.
- f: To be performed within 24 hours prior to dosing.
- g: Baseline 24hr PK will only be conducted on study drug naïve individuals.
- h: Prior to dosing.
- i: Participants will return to NIH CC on Day 27 for scheduled events. Participants will be observed and examined one day post cessation of dosing, for any withdrawal effects. Administration of the final dose and 24 hour PK will occur following approximately 28 days dosing (not to exceed 30 days).
- j: Approximately 14 days (\pm 2 days) following cessation of S 48168 (ARM210), participants will have follow-up safety laboratory tests.

Abbreviations: Admin = Administration, AE = Adverse event(s), C-I = Check-in, Chem = Chemistry, CYP = Cytochrome P450, FU = Follow-up, HIV = Human immunodeficiency virus, NIH CC = National Institutes of Health Clinical Center, PI = Principal Investigator, PK = Pharmacokinetics.

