10.2 Study Endpoints

Primary endpoint:

Composite safety and tolerability profile

(Frequencies of the following: TEAEs \geq grade 2 in severity (CTCAE version 5), all SAEs, and all AESIs).

Exploratory Endpoints:

S 48168 (ARM210) pharmacokinetics

Day 1 composite PK profile (for study drug naïve participants only)

(Comprised of the following: AUC0-t, AUC0-inf, Cmax, Tmax, and t_{1/2}).

Day 28 (not to exceed Day 30) composite PK profile

(Comprised of the following: AU_{tau}, Cmax, Tmax, Cmin, RAAUC, and RACmax).

S 48168 (ARM210) pharmacodynamics

RyR1-calstabin1 binding

(Change from baseline in RyR1-calstabin1 binding (arbitrary units)).

RyR1 channel integrity

(Change from baseline in RyR1-mediated Ca²⁺ leak (arbitrary units)).

Muscle/motor function and fatigue

Hand grip strength (kg), pinch strength (kg).

Time taken to complete each of the following (seconds): walk 10-meters, supine to stand, ascend 4 stairs, and descend 4 stairs.

MFM-32 score for domains 1, 2, 3, and total (% of maximum score).

PROMIS-fatigue subscale score (t-score).

Quantitative muscle strength (kg)

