A study investigator will contact participants by telephone weekly when not on site to remind them of upcoming, scheduled local phlebotomy appointments and perform remote TEAE assessments, if applicable.

The final onsite study visit (Day 42 ± 2 Days) will consist of muscle/motor function assessments, PROMIS-fatigue questionnaire, AE assessment, vital signs, physical examination, safety labs, and a blood draw.

Daily subject diaries will be used to capture both time of dose administered as well as any symptoms they may feel in between remote TEAE assessments.

Confinement, Return Visits, and Follow-Up

Participants will be admitted to the NIH CC on the evening of Day -1 for drug administration. Drug naïve participants will undergo baseline 24hr PK sample collection the next morning.

Participants will attend a phone call on Day 14 (± 2 days). This will include review of any concomitant medication, TEAE assessment, and C-SSRS and PROMIS-fatigue questionnaires. Safety labs will be obtained remotely or at NIH CC if the participant is local to the study site.

Participants will return to the NIH CC on Day 28 (± 1 day) for repeat safety labs, PE, ECG, vital signs, and a 24hr PK sample collection.

Participants will return to the NIH CC for Day 42 ± 2 days for vital signs, AE assessment, exploratory efficacy assessments, safety labs, and a blood draw.

At all times, a subject may be required to remain at the NIH CC for longer at the discretion of the Principal Investigator (PI) or designee (e.g. when deemed necessary for safety reasons).

Participants will be contacted by telephone/secured email for a follow up regarding TEAEs approximately weekly when not on site and will also have a blood draw for safety clinical laboratory tests at day 14. This will include participants who terminate the study early. Participants local to the study site will have the option of completing AE assessments and safety clinical laboratory tests at the NIH.

Participants will also be able to enter any symptoms they experience in a participant diary (Appendix # 6).

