12.10.7.2 Expected Adverse Events

Previous adverse events include stomach pain, diarrhea, vomiting, constipation, nausea, dry mouth, loss of taste, catheter site pain, fatigue, nose and throat pain, muscle stiffness, lower back pain, dizziness, headache, local numbness, and excessive sweating. A complete list of previous adverse events, which may be expected in this trial, are provided in the Investigator's Brochure.

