13.3 Safety Evaluation

All safety data will be populated in the individual CRFs. All safety data will be listed by subjects.

Dosing dates and times will be listed by subject in their diary when not confined to the NIH CC.

AEs will be coded using the most current version of Medical Dictionary for Regulatory Activities (MedDRA®) available at Celerion and summarized by cohort and treatment for the number of subjects reporting the Treatment Emergent Adverse Events (TEAE) and the number of TEAEs reported. A by-subject AE data listing including verbatim term, coded term, treatment, severity, and relationship to treatment will be provided.

Safety data including ECGs, vital signs assessments, clinical laboratory evaluations, will be summarized by treatment and point of time of collection.

Descriptive statistics using appropriate summary statistics will be calculated for quantitative safety data as well as for the difference to baseline, when appropriate.

Concomitant medications will be listed by subject and coded using the most current version of WHO drug dictionary available at Celerion. Medical history will be listed by subject.

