6.3 Adverse Events

All adverse events (AEs) reported during this clinical trial will be coded using the Medical Dictionary for Regulatory Activities (MedDRA[®]), Version 21.0.

All adverse events will be reviewed by the Medical Monitor and graded in accordance with CTCAE version 5

(https://ctep.cancer.gov/protocoldevelopment/electronic_applications/ctc.htm)

All AEs captured in the database will be listed in by-subject data listings including verbatim term, coded term, treatment, severity, relationship to study medication, and action; however, only treatment-emergent AEs (TEAEs) will be summarized.

A TEAE is defined as an AE that is starting or worsening at the time of or after study drug administration. Each TEAE will be attributed to a treatment based on the onset date and time of the AE.

An AE will also be considered treatment emergent if: onset date of an AE is missing; if onset time of an AE is missing and the onset date is the same as the treatment dosing date; and if both AE onset date and time are missing.

TEAEs will be tabulated by System Organ Class (SOC) and Preferred Term (PT). Summary tables will include number of subjects reporting the AE and as percent of number of subjects dosed by treatment and study overall. The number of AEs will be tabulated in a similar manner. Tables which tabulate the number of TEAEs by severity and relationship to study treatment will also be included.

Serious adverse events (SAEs), if present, will also be listed. Applicable narratives will be included in the CSR.

Frequencies of TEAEs \geq grade 2 in severity (CTCAE version 5), all SAEs, and all AE of Special Interest (AESI) will be tabulated by SOC/TE.

The frequency and severity of clinically significant AEs will be compared descriptively between treatment and historical controls including a previously conducted natural history study at the NIH.

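### With no CTCAE-graded symptom record before dosing, and a missing-onset rule that makes no exception for documented history, a chronic RYR1-RM symptom can enter the grade 2 or higher TEAE endpoint by three routes

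*Protocol*

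**What the plan says.** **Endpoint.** Protocol 10.2 defines the primary endpoint as the frequencies of TEAEs of at least "grade 2 in severity (CTCAE version 5), all SAEs, and all AESIs". Relatedness to drug is not part of it. SAP Table 14.3.1.4 reports it.

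**Collection window.** Protocol 12.10.7.4 states: "The reporting period for AEs is the period immediately following each study administration through 28 days after each dose". The same section opens by sending every AE of the study to the AE CRF, and footnote e of the flow chart (Protocol 7) says "AE's will be monitored throughout the study". The flow chart starts TEAE monitoring on Day 1 and the diary on Day 2. On the diary, Protocol 11.1 says: "Daily subject diaries will be used to capture both time of dose administered as well as any symptoms they may feel".

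**Classification.** SAP 6.3 states: "A TEAE is defined as an AE that is starting or worsening at the time of or after study drug administration". It adds: "An AE will also be considered treatment emergent if: onset date of an AE is missing". Only TEAEs are summarized; other AEs are listed.

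**Information before dosing.** Medical history is taken at screening (Protocol 12.4), with an interim history for re-enrolled participants (12.2). In the analysis, "Medical history will be listed by subject" (Protocol 13.3); SAP 8.10 adds MedDRA coding. PROMIS-fatigue is completed on Day -1 (SAP 8.2). Physical examination and motor and strength tests also precede dosing. None of these is said to carry a CTCAE grade or to feed into TEAE classification.

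**Overlap with the disease.** The expected AEs in Protocol 12.10.7.2 include "fatigue, nose and throat pain, muscle stiffness, lower back pain, dizziness, headache".

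**The concern.** Whether an event is treatment-emergent decides whether it counts in the grade 2 or higher component. That decision needs either a reliable onset date or a pre-dose severity to compare with. Fatigue, stiffness and back pain are plausible long-standing complaints in a congenital myopathy. The protocol presumes fatigue before dosing, since Protocol 10.1 expects the drug to reduce it. Such symptoms are hard to date and may fluctuate.

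Questioning is also uneven. On study drug, participants get open-ended and focused safety questions (Protocol 12.10.7.3), and no matching interview is scheduled before the first dose. An old symptom may then be voiced for the first time on drug.

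The plan does set a baseline elsewhere: for the transaminase criterion among the AESIs, for laboratory shift tables, and for blood pressure and pulse. It sets none for symptoms. With no concurrent control arm, background symptoms counted as TEAEs cannot be subtracted.

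**Working it through.** **Step 1. How a chronic symptom mentioned on drug is classified under SAP 6.3.**

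| What is recorded | TEAE? | Why |
|---|---|---|
| Pre-dose onset date, severity unchanged | No | Neither starts nor worsens after dosing |
| Onset date blank | Yes | Missing-onset rule, with no check against history |
| Onset entered as the date of first report | Yes | Apparent onset is after dosing |
| Pre-dose onset, judged worse | Yes | Worsening, with no stated reference |

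The first row works as intended. The other three are the routes by which a background symptom can enter. SAP 6.3 gives no rule for a partial date, such as a year alone.

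**Step 2. Could existing pre-dose information settle the last three rows?** In part. Medical history could show that the symptom was present, but the SAP only codes and lists it. PROMIS-fatigue gives a score for one symptom; it is not a CTCAE grade. Protocol 12.10.7.4 specifies CTCAE grading for reported AEs only. The information could help, but no rule uses it.

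**Step 3. Does causality review remove such an event?** No. Protocol 12.10.7.4 has the investigator weigh concomitant disease and history when judging relatedness, but the endpoint counts TEAEs whatever their relatedness.

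**Step 4. Size.** There is no planned figure to reproduce: Protocol 13.2.1 gives n = 8 without event rate, margin, alpha or power. The target is 8–20 completers, and 3 participants had been dosed in each group at the time of writing.

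- Shift in subject-level frequency from one misclassified participant = 1/n: 1/3 = 33.3 points, 1/8 = 12.5 points, 1/20 = 5 points.
- Exact (Clopper–Pearson) 95% interval at 0/8: upper limit 1 − 0.025^(1/8) = 0.369, so 0–36.9%.
- At 1/8: lower limit 1 − 0.975^(1/8) = 0.003; upper limit is the 97.5th percentile of Beta(2, 7) = 0.527, so 0.3–52.7%.

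The SAP plans no such intervals; they are given for scale.

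**Step 5. Chance of at least one such participant.** Assumption: each participant independently has probability p of at least one chronic symptom misclassified as a grade 2 or higher TEAE. The documents give no value for p, so a range is shown. P(at least one) = 1 − (1 − p)^n.

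| p | n = 3 | n = 8 | n = 20 |
|---|---|---|---|
| 0.05 | 14.3% | 33.7% | 64.2% |
| 0.10 | 27.1% | 57.0% | 87.8% |
| 0.20 | 48.8% | 83.2% | 98.8% |
| 0.30 | 65.7% | 94.2% | 99.9% |

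**The case against.** The strongest reply is that the plan already handles the ordinary case. Protocol 12.10.7.4 requires an onset date for each AE, and a lifelong symptom has an onset known to precede dosing even if the day is not known. That stands. A reader might infer that any chronic symptom first recorded on drug becomes a TEAE; the SAP definition does not support this.

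A reader might also infer that nothing is collected before dosing. The documents do not support that either. Two sentences describe a wider window than the one in 12.10.7.4, a TEAE row cannot begin before treatment, and history and Day -1 PROMIS-fatigue exist. The CRF listing shells are deferred, and the AE script, diary and medical monitoring plan are not among the documents, so the CRF may hold more than the text specifies. What remains is that the text ties none of it to TEAE classification.

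The missing-onset rule is conservative: it inflates counts and does not hide harm. That stands for that rule. A judgement of worsening without a reference can err either way.

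The consequences are bounded. The analysis is descriptive, the medical monitor and DSMB see the AEs, and the AE-based termination criteria in Protocol 11.8.5 require relatedness, so a misclassified TEAE does not trigger them by itself. The planned natural-history comparison helps only in part, because its AE collection rules are not described.

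A stricter remedy, counting only a higher CTCAE grade, would drop real worsening within a grade, and fatigue and stiffness are also expected drug AEs. That objection is sound and shapes the fix.

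**Conclusion.** The point holds within limits. The plan specifies no CTCAE-graded symptom record before dosing, leaves worsening without a reference, and applies the missing-onset rule even to symptoms documented beforehand. Three routes into the grade 2 or higher component follow; a stable symptom with a known pre-dose onset is not among them.

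The firm part of the size is arithmetic: one misclassified participant is worth 12.5 points at n = 8 and 5 points at n = 20. How often this would happen is unknown. The probabilities in the working rest on an assumed p and on independence between participants.

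It is tempting to compound a reporting chance over the weekly contacts. That would model reporting, not misclassification, and would treat repeated mentions of one persistent symptom as independent. The documents support no such figure.

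The change is worth making because it is cheap and the primary endpoint is uncontrolled and small.

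**What to change.** 1. In Protocol 12.10.7.4, reconcile the reporting-period sentence with the section's opening sentence and footnote e of the flow chart. State one start point for AE recording, before the first dose.
2. For remaining participants, and before each re-enrolled course, give the existing AE script (Appendix 5) at Day -1 and record each ongoing symptom with its CTCAE v5 grade.
3. In SAP 6.3, judge worsening against that record, counting either a grade increase or a worsening within a grade that the investigator documents. Apply the missing-onset rule only to events not documented before dosing in the Day -1 record or the medical history.
4. For the six participants already dosed, use screening medical history as the reference for those courses. Repeat the primary table under SAP 6.3 as it now stands, as a sensitivity analysis.

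The cost is an estimated 10 minutes and one CRF page per course, plus short edits to both documents. Unchanged pre-existing symptoms move from the TEAE tables to the listings. The reference also differs between earlier and later participants, which the report should state; the sensitivity table, with one rule for all, shows whether it matters.

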12.10.7.5 Serious Adverse Event

If any AEs are serious, as defined by the FDA Code of Federal Regulations (CFR), Chapter 21, special procedures will be followed. All SAEs will be reported to the Sponsor per the medical monitoring plan (Appendix # 17) and adhere to 21 CFR 312.32 for Investigational New Drugs (IND) and to the Guidance for Industry and Investigators: Safety Reporting Requirements for INDs and BA/BE, dated December 2012 (FDA 2012). Reporting of SAEs to the IRB will be consistent with NIH Policy 801.

A SAE is any AE or suspected adverse reaction that in the view of either the PI (or designee) or Sponsor, results in any of the following outcomes: Death, a life-threatening adverse event, inpatient hospitalization or prolongation of existing hospitalization, a persistent or significant incapacity or substantial disruption of the ability to conduct normal life functions, or a congenital anomaly/birth defect. Important medical events that may not result in death, be life-threatening, or require hospitalization may be considered serious when, based upon appropriate medical judgment, they may jeopardize the patient or subject and may require medical or surgical intervention to prevent one of the outcomes listed in the above definition. Examples of such medical events include allergic bronchospasm requiring intensive treatment in an emergency room or at home, blood dyscrasias or convulsions that do not result in inpatient hospitalization, or the development of drug dependency or drug abuse.

Life-threatening is defined as an AE or suspected adverse reaction that in the view of the PI (or designee) or Sponsor, its occurrence places the patient or subject at immediate risk of death. It does not include an adverse event or suspected adverse reaction that, had it occurred in a more severe form, might have caused death.

Unexpected is defined as an AE or suspected adverse reaction that is not listed in the IB or is not listed at the specificity or severity that has been observed; or is not consistent with the risk information described in the general investigational plan or elsewhere in the current application, as amended.

12.10.7.6 Reporting of Unanticipated Problems, Adverse Events, and Protocol Deviations

The Principal Investigator is responsible for detecting, documenting, and reporting unanticipated problems, AEs, including SAEs, and deviations in accordance with NIH policy, IRB requirements, and federal regulations. Relatedness to the research of all serious adverse events will be determined by the PI in consultation with the medical monitor.

Reporting of unanticipated problems, adverse events, and protocol deviations will be reported to the IRB as detailed in NIH Policy 801.

Within 24 hours of identifying a SAE, regardless of the presumed relationship to the study product, the PI must complete the serious adverse event (SAE) case report form and email it to [REDACTED] as ARMGO representative according to the requirements of 21 CFR 312.64(b) and as agreed upon with the sponsor.

The PI will record nonserious AEs and report them to the Sponsor as agreed upon in the Medical Monitoring Plan (Appendix # 17). All expedited AE reports will be processed by ARMGO with Celerion.

12.10.7.7 AE's of Special Interest

An AE of Special Interest (serious or nonserious) is one of scientific and medical concern specific to the compound or program, [REDACTED]

AEs of special interest in this trial include:

- Large increases in transaminases, Aspartate aminotransferase or Alanine aminotransferase. If the subject's baseline transaminases were within normal limits, then a change of 3X ULN is the criteria. If the subject's baseline transaminases are above the ULN at baseline, then 5X ULN would be the criteria. Baseline elevations in transaminases have been known to occur in some patients with *RYR1*-RM, likely due to muscle injury as a consequence of the disease and normal activity.
- CNS toxicity (tremors/convulsions seen in safety assessment animals) - consider tremors and any symptoms of seizure as the events to monitor for.
- Gastric toxicity - severe gastric or epigastric pain or severe vomiting.
- Plasma Cmax (S 48168) >35 µg/mL.

